3.3 Outcome measures/endpoints

3.3.1 Primary endpoint

The proportion of eligible donor cardiac allografts that are randomised and receive the correct intervention. This is a composite outcome. For the purposes of this study, eligible cardiac allografts are defined as hearts from adult (age>18 at time of donation) DBD donors, where an offer has been made to an adult (age>18 at time of transplant procedure) recipient at a UK transplant centre and the donor cardiac allograft is retrieved from the donor and implanted into the recipient. The composite outcome, therefore, is defined by the product of the following proportions:

- i. The proportion of eligible donor cardiac allografts where the recipient has consented to take part in this study.
- ii. The proportion of (i.) where randomisation occurs according to the Protocol.
- iii. The proportion of (ii.) where the heart is preserved in the allocated preservative solution.

We feel this composite outcome provides the best estimate of the feasibility of the larger trial. A proportion that falls within or above the upper limit of the 95% Jeffreys credible interval defined assuming that a probability of 2/3 of meeting the primary target and a sample size of 50 will be considered a success, as it would indicate the potential to recruit approximately 80 hearts per year, a yearly number corresponding to a probability of 0.85 (power) of detecting the primary effect in the 5-

F-CUSToS Protocol

Version Number 2.0; Dated 30 January 2025

year main study. A proportion that falls below the 95% credible interval of two-thirds of eligible donor cardiac allografts but above one-third would be considered potentially successful, with the option to continue to perform the randomised controlled efficacy trial, providing appropriate changes can be made to address any concerns.

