3.3.2 Secondary endpoints

- i. The proportion of eligible recipients who consent to take part in the study.
- ii. The proportion of eligible donor cardiac allografts where randomisation occurs according to the Protocol.
- iii. The proportion of eligible donor cardiac allografts where the heart is preserved in the correct randomly allocated solution.
- iv. Key outcome completeness
- v. The development of Primary Graft Dysfunction, according to the 2014 ISHLT Consensus Definition(2), within 24 hours of transplant implantation.
- vi. Echocardiographic parameters from trans-oesophageal echo immediately after transplant implantation, including:
 - a. Left Ventricular ejection fraction
 - b. Left ventricular maximal posterior wall thickness
 - c. Maximal septal wall thickness
 - d. Left ventricular function
 - e. Right ventricular function
 - f. The presence/absence of regional wall motion abnormalities
- vii. 30-day all-cause mortality.
- viii. 6-month survival rates, determined at the end of the study.
- ix. Development of the following post-operative complications will be recorded:
 - a. Dysrhythmias (defined by the clinical team) within 30-days of transplant implantation
 - b. Myocardial Infarction (defined according to ESC definitions of myocardial infarction post cardiac surgery) within 30-days of transplant implantation
 - c. Stroke (defined by radiological evidence of ischaemia/haemorrhage and clinical symptoms of stroke) within 30-days of transplant implantation
 - d. Transplant rejection (defined by the clinical team and confirmed on histopathology of biopsy material or post-mortem) within 30-days of transplant implantation
 - e. The need for post-operative renal replacement therapy within 30-days of transplant implantation
 - f. Infection (from any source requiring antibiotic therapy) within 30-days of transplant implantation
 - g. Venous thromboembolism (defined by radiological evidence and need for treatment) within 30-days of transplant implantation
 - h. Re-admission to any UK hospital within 30 days of transplant implantation
 - i. Hyponatraemia within 24 hours of transplant implantation (Na<125mEq/L on any serum laboratory-analysed sample, not blood gas analysis)
- x. Median length of initial ICU stay in hours
- xi. Median length of initial hospital stay in days

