4 TRIAL DESIGN

This is a feasibility study of a single-blind, national, multi-centre, randomised controlled trial. The purpose of the trial is to assess the methodology and feasibility of conducting an appropriately powered efficacy randomised controlled trial comparing Custodiol-HTK with St Thomas' solution for donor cardiac allograft preservation during cardiac transplantation. The design, therefore, replicates a larger efficacy randomised controlled trial, differing only in its primary outcome, as described above.

The trial will be conducted at all six UK adult cardiothoracic transplant centres. Donor hearts included in the study will be randomly allocated on a 1:1 basis to receive either Custodiol-HTK or St Thomas' solution as cardioplegia and preservative solution during the organ retrieval process. Participants (recipients of donor cardiac allografts that have received one of the above treatments as part of the random allocation process) will be blinded to their treatment allocation. It is not possible to blind the healthcare staff involved in the transplant process as the solutions have different volumes and methods of administration and are different colours. Healthcare staff who look after the recipient but were not directly involved in the transplant retrieval or implant procedures should not be informed of the treatment allocation.

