10.2 Planned recruitment rate

A proportion of two-thirds for the primary outcome will be considered successful, as it would correspond to a yearly average of approximatively 80 patients being recruited in the main study, assuming a yearly number of available hearts of 120 (corresponding to the yearly observed number of adult DBD heart transplants in the UK during the last two years).

A power calculation for a superiority trial based on the development of primary graft dysfunction as the primary outcome showed that a sample size of 400 patients would allow detection of a 14% absolute risk reduction in PGD between the two solutions of interest (from 36% to 22%) corresponding to an odds ratio of 0.5 (or 17 cases of PGD prevented per year) with a probability (power) of 0.85 with a type I error of 0.05 when considering a two-sided test of difference in proportions. As approximately 120 adult DBD heart transplants are performed in the UK each year, we estimate that the larger trial will take 5 years to complete (i.e., $80 \times 5 = 400$).

For this feasibility trial to meet its recruitment target, we anticipate a recruitment rate of 80 patients per year, over a period of 6-12 months. 1 patient per site per month would result in a 9-month recruitment period.

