10.7 Participant population

The primary outcome will be analysed on an intention to treat basis. Secondary outcomes will be analysed "as randomised".

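### The success rule in section 3.3.1 counts a randomised heart given the wrong solution as a lost recruit, so a composite of two-thirds does not fix the main trial's power at 0.85

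*Protocol*

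**What the plan says.** Section 3.3.1 sets the primary endpoint: "The composite outcome, therefore, is defined by the product of the following proportions". The components are (i) consent among eligible hearts, (ii) randomisation among those consented, and (iii) "The proportion of (ii.) where the heart is preserved in the allocated preservative solution".

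Success is judged on the product. A value within or above a 95% Jeffreys interval around two-thirds "will be considered a success, as it would indicate the potential to recruit approximately 80 hearts per year", which section 3.3.1 describes as "a yearly number corresponding to a probability of 0.85 (power) of detecting the primary effect in the 5"-year main study. Section 10.2 supplies the power statement: "a sample size of 400 patients would allow detection of a 14% absolute risk reduction in PGD between the two solutions of interest". The PGD rates behind it are 36% and 22%, with power 0.85, two-sided 0.05, and 120 available hearts a year.

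Three other places bear on the point:
- Section 4 says of this study: "The design, therefore, replicates a larger efficacy randomised controlled trial, differing only in its primary outcome".
- Section 10.7: "Secondary outcomes will be analysed" as randomised. PGD is one of those outcomes.
- Section 3.3.2 lists as secondary endpoint iii: "The proportion of eligible donor cardiac allografts where the heart is preserved in the correct randomly allocated solution". Its denominator is eligible hearts, and no threshold is attached.

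**The concern.** Failures of (i) and (ii) reduce enrolment, so turning them into hearts per year is sound. A failure of (iii) is different in kind. The heart is already in the trial, and its recipient contributes a PGD outcome to the allocated arm after receiving the other arm's solution. The rule scores that heart as if it had never been recruited. For the power of an as-randomised comparison it is worse than that, because it pulls the two arms together.

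The result of this rule is meant to justify a five-year national trial. If high consent offsets imperfect adherence, the composite can reach two-thirds while the power attached to that figure no longer holds. Section 7.9 foresees wrong-solution hearts and collects the reasons for them, but the decision rule does not respond to how often they occur.

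**Working it through.** **Inputs.** PGD 36% vs 22%, 400 hearts, two-sided 0.05, power 0.85, 120 hearts a year over 5 years (section 10.2); 1:1 allocation (section 4); only two solutions in UK use (section 1). The crossover share f among randomised hearts is an assumption, shown from 0 to 20%. A crossed-over heart is assumed to carry the PGD risk of the solution it received.

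**Step 1: reproduce the stated power.** With n per arm, mean rate p and difference d, the pooled normal test gives

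power = Φ{[d√n − 1.96√(2p(1−p))] / √(p1(1−p1) + p2(1−p2))}.

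At n = 200, p1 = 0.36, p2 = 0.22: (0.14 × 14.142 − 1.96 × 0.6417) / 0.634 = 1.139, so power is 0.873. Fisher's exact test at 200 per arm gives 0.851, and the continuity-corrected sample size for 0.85 is 202 per arm. The stated figures therefore reproduce, on the premise that every randomised heart receives its allocated solution.

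**Step 2: dilution.** If shares f1 and f2 of the two arms receive the other solution, the as-randomised difference is 14 × (1 − f1 − f2) points. With equal arms and pooled share f = (f1 + f2)/2, this is 14 × (1 − 2f), however the failures divide between arms.

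**Step 3: hearts randomised when the composite is exactly two-thirds.** Composite = randomised share × (1 − f). Hearts randomised in 5 years are therefore 600 × (2/3)/(1 − f) = 400/(1 − f). The rule's own arithmetic is thus credited with the extra randomised hearts.

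**Step 4: power at that composite (pooled normal test).**

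| f | Hearts randomised | Difference (points) | Power, crossover split evenly | Power, all crossover in the lower-rate arm |
|---|---|---|---|---|
| 0 | 400 | 14.0 | 0.873 | 0.873 |
| 2% | 408 | 13.4 | 0.852 | 0.850 |
| 5% | 421 | 12.6 | 0.815 | 0.810 |
| 10% | 444 | 11.2 | 0.741 | 0.729 |
| 20% | 500 | 8.4 | 0.544 | 0.523 |

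For f = 10%, split evenly, the rates are 0.346 and 0.234 with 222.2 per arm: (0.112 × 14.907 − 1.96 × 0.6417) / 0.6368 = 0.647, so power is 0.741.

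Fisher's exact test, even split, gives 0.851, 0.787, 0.708 and 0.506 at f = 0, 5%, 10% and 20%.

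**Step 5: sample size for 0.85 (pooled test, even split).** 376 at f = 0, 464 at 5%, 588 at 10%, 1,046 at 20%.

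**The case against.** The case on the other side has real weight.

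- **Crossover is not hidden.** A reader might infer that no endpoint reveals it. That is not so. Component (iii) is adherence among randomised hearts, and secondary endpoints ii and iii share the eligible-heart denominator, so iii divided by ii gives the same quantity. Section 7.7 records the treatment applied, section 7.9 the reason for any wrong treatment, and section 8.13 reviews each randomised case. This stands: the gap lies in the decision rule, not in the data or the reporting.
- **The size rests on an assumed rate.** The protocol gives no crossover rate, and its procedures work against crossover: randomisation follows acceptance of the heart, every retrieval team carries both solutions, and both sets of instructions are covered in the briefing (section 7.3). At 2% the loss is negligible. This stands too, but a feasibility study is where the rate is learned, and its rule should respond to it.
- **Direction.** One might infer that failures will fall mainly in the Custodiol-HTK arm because St Thomas' is the usual solution. The documents do not support this. The 90% figure in section 1 describes practice outside the trial, and the fallback in section 7.2.4 concerns hearts that are never randomised. The dilution does not depend on direction.
- **A higher threshold.** It would be wrong to say that a higher threshold could not help. Adherence cannot be lower than the composite, so a higher threshold does cap crossover, though inefficiently.
- **Fixed sample size.** Computing power at 400 whatever the value of f would overstate the loss, since a composite of two-thirds implies 400/(1 − f) randomised hearts. The table uses the latter.
- **Main-trial analysis set.** It is inferred from sections 4 and 10.7, not stated. Excluding crossed-over hearts would avoid the dilution but abandon the as-randomised comparison.

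**Conclusion.** The point holds as a defect in the decision rule. A composite of exactly two-thirds does not correspond to one level of power. On the pooled test it is compatible with 0.87 at no crossover, 0.85 at 2%, 0.81-0.82 at 5%, 0.73-0.74 at 10% and 0.52-0.54 at 20%. The stated link to 0.85 is safe only with near-full adherence: up to about 2% crossover by the pooled test and essentially none by Fisher's exact test.

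This rests on three assumptions: the value of f; that a crossed-over heart takes on the risk of the solution it received; and that the main trial analyses PGD as randomised. It does not show that crossover will be common, that it would go unseen, or that it would favour one arm.

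**What to change.** In section 3.3.1:

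1. Base the conversion to 80 hearts a year on (i) × (ii).
2. Make pooled adherence (iii) among randomised hearts a separate progression criterion, judged on the point estimate with its Jeffreys interval.
3. State that main-trial power or sample size will be recalculated with the observed crossover through (1 − 2f).
4. Report adherence by arm descriptively only, and keep reporting the composite.

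The cost is protocol wording; the data are already collected under sections 7.7 and 7.9. The downside is that success becomes harder to declare and the adherence estimate is imprecise. With 50 randomised hearts and no failures, the Jeffreys 95% upper bound for crossover (97.5% point of Beta(0.5, 50.5)) is about 4.9%. With 25 in one arm and no failures it is about 9.5%. A by-arm limit near 5% could therefore not be confirmed even with perfect adherence, which is why the criterion should be pooled.

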3 OBJECTIVES AND OUTCOME MEASURES/ENDPOINTS

3.1 Primary objective

To assess the feasibility of conducting a national, single-blind, randomised controlled efficacy trial comparing the effect of using Custodiol-HTK or St Thomas' solution as cardioplegia and preservative solution during cardiac transplantation of UK DBD donor hearts on the rate of PGD.

Hypothesis:

It is feasible to conduct the above trial in the UK within 5 years.

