10 STATISTICS AND DATA ANALYSIS

10.1 Sample size calculation

This is a feasibility study, so formal sample size calculation is not required. However, 50 hearts will give a 95% confidence interval of 53%-79% assuming a primary outcome rate of 66%.

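### The success cut in 3.3.1 sits at about 53%, but its stated justification (80 hearts a year, power 0.85 in 5 years) holds only near two-thirds

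*Protocol*

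**What the plan says.** Protocol 3.3.1 sets three outcomes for the feasibility proportion. Success is "A proportion that falls within or above the upper limit of the 95% Jeffreys credible interval defined assuming that a probability of 2/3", where the interval is the one for 50 hearts. The reason given is "as it would indicate the potential to recruit approximately 80 hearts per year", which the same sentence equates with power 0.85 in the 5-year main study. The middle category reads: "A proportion that falls below the 95% credible interval of two-thirds of eligible donor cardiac allografts but above one-third would be considered potentially successful".

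Protocol 10.1 prints the interval: "50 hearts will give a 95% confidence interval of 53%-79% assuming a primary outcome rate of 66"%. Protocol 10.2 links the yearly number to the target itself: "A proportion of two-thirds for the primary outcome will be considered successful, as it would correspond to a yearly average of approximatively 80 patients", on the assumption of 120 available hearts a year. It plans a 400-patient main trial to detect 36% versus 22% primary graft dysfunction with power 0.85, two-sided 5%. The hypothesis in 3.1 is: "It is feasible to conduct the above trial in the UK within 5 years".

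**The concern.** The rule and its reason refer to different proportions. The reason is the arithmetic of two-thirds: two-thirds of 120 is 80, and 80 a year for 5 years is 400. The rule admits every result down to the lower end of an interval around two-thirds. Failure to exclude two-thirds is thus treated as if it showed two-thirds.

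The primary objective is to judge whether the main trial is feasible, and this rule delivers that judgement. A result just above 53% would be reported as a success, with a protocol statement attached that it indicates 80 hearts a year and power 0.85. The observed rate would support neither figure, and would not support completion within the 5 years of the hypothesis.

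**Working it through.** **Inputs.** Target 2/3 and n = 50 (3.3.1); printed interval 53%-79% (10.1); 120 hearts a year, 400 patients, 36% versus 22%, power 0.85, two-sided 0.05 (10.2); 1:1 allocation (section 4); 5 years (3.1).

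**1. Reproduce the interval.** The equal-tailed Jeffreys interval is given by the 2.5% and 97.5% quantiles of Beta(x + 0.5, n − x + 0.5). With x = 50 × 2/3 = 33.33 this is Beta(33.83, 17.17), giving 52.95% to 78.5%. With x = 33 the lower limit is 52.3%. The printed 53%-79% is reproduced to rounding.

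**2. Locate the cut.** Results inside or above the interval succeed, and only results below it drop to the middle category. The cut is therefore the lower limit, about 53%. With 50 as the denominator, 26/50 = 52% falls short and 27/50 = 54% passes.

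**3. Reproduce the main-trial calculation.** For two proportions with n per arm and mean proportion p̄ = (0.36 + 0.22)/2 = 0.29:

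power = Φ{ [0.14 − c − 1.96 √(2 p̄(1 − p̄)/n)] / √[(0.36×0.64 + 0.22×0.78)/n] }

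Here c = 1/n with the continuity correction and c = 0 without it. At n = 200 the corrected power is 0.848 and the uncorrected power is 0.873. Solving for 0.85 gives 202 per arm (404) corrected and 188 per arm (376) uncorrected. The corrected version reproduces the protocol's pairing of 400 patients with 0.85.

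**4. Apply the protocol's own conversion (proportion × 120) at the cut and at the target.**

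| Observed proportion | Hearts a year | In 5 years | Power, corrected | Power, uncorrected | Years to 400 |
|---|---|---|---|---|---|
| 53% | 63.6 | 318 | 0.750 | 0.788 | 6.3 |
| 54% (27/50) | 64.8 | 324 | 0.759 | 0.796 | 6.2 |
| 66% (33/50) | 79.2 | 396 | 0.844 | 0.869 | 5.05 |
| 2/3 | 80 | 400 | 0.848 | 0.873 | 5.0 |
| 68% (34/50) | 81.6 | 408 | 0.855 | 0.879 | 4.9 |

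The shortfall against 80 at the cut is (80 − 64.8)/80 = 19% to (80 − 63.6)/80 = 20.5%.

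**5. How often the rule declares success**, taking 50 as the number of eligible hearts and X ~ Binomial(50, p):

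- P(X ≥ 27) = 0.34 at p = 0.50 (60 hearts a year)
- P(X ≥ 27) = 0.61 at p = 0.55 (66 a year)
- P(X ≥ 27) = 0.98 at p = 2/3 (80 a year)

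At 27/50 the Jeffreys posterior, Beta(27.5, 23.5), puts a probability of 0.03 on a true rate of at least 2/3.

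**6. Cost of a cut near two-thirds**, at a true rate of 2/3: P(X ≥ 33) = 0.60 and P(X ≥ 34) = 0.49, against 0.98 for the present rule.

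**The case against.** The best defence is that the protocol chose a tolerant rule openly. The interval is printed, the wording speaks of potential and of an approximate number, and with about 50 hearts some allowance for sampling error is reasonable: a programme whose true rate is two-thirds passes 98% of the time. A cut on the point estimate would not prove 80 a year either. This stands as far as the choice of cut goes, because how lenient to be is a design preference. It does not rescue the justification, which attaches a specific yearly number and power to every success.

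A reader might infer that 10.2 lays down a second, contradictory rule. The text does not go that far. It says that two-thirds counts as successful, not that only two-thirds or more does, and two-thirds also succeeds under 3.3.1. Section 10.2 is better read as the target and 3.3.1 as the tolerance around it, though the two are not cross-referenced.

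A reader might also conclude that 32/50 is the lowest cut that supports the claim, since the uncorrected formula needs only 376 patients. But the formula that reproduces the protocol's 400 gives 0.832 at 32/50 (384 patients), below 0.85.

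Finally, 50 may be the number recruited rather than the number of eligible hearts, since the trial summary plans 50 patients and 10.2 describes a recruitment target. The counts and probabilities in steps 5 and 6 would then change. The percentage cut, and the yearly figures at it, would not.

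**Conclusion.** The justification in 3.3.1 is wrong at the rule's own threshold. At 53-54% the implied yield is about 64-65 hearts a year, about a fifth below 80. That means 318-324 patients in 5 years, with power about 0.75-0.76 (0.79-0.80 uncorrected), or about 6.2-6.3 years to reach 400. These figures rest on the protocol's 120 hearts a year and its 36% versus 22% effect. The success probabilities of 0.34 and 0.61 rest also on 50 being the eligible-heart denominator.

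It would be too strong to say that the rule makes the trial's conclusion invalid. The observed proportion will be reported with its own interval (10.3.2), so a result near 54% would be visible. The estimate is not biased, no participant is affected, and a middle category already exists. The fault is an over-claim attached to the primary decision rule. It should be fixed before the rule is applied.

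**What to change.** Amend 3.3.1 in one of two ways, and cross-reference 10.2 to the rule chosen.

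- **Keep the 53% cut.** Remove the claim of 80 a year and power 0.85 as the reason for success. State instead that the cut shows only compatibility with two-thirds, and that at the cut one would expect about 64 hearts a year, about 320 in 5 years, power about 0.75 (0.79 without continuity correction), or about 6.3 years to reach 400. The cost is wording only.
- **Keep the claim.** Tie outright success to an observed proportion of about two-thirds, and place 53% to two-thirds in the existing potentially successful zone. The cost is real: at a true rate of two-thirds and 50 eligible hearts, outright success falls from about 98% to about 60% (33/50) or 49% (34/50). Nearly all the remainder falls in the zone where the main trial may still proceed with changes.

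In either case, say whether 50 counts eligible hearts or recruited patients.

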3.3.2 Secondary endpoints

- i. The proportion of eligible recipients who consent to take part in the study.
- ii. The proportion of eligible donor cardiac allografts where randomisation occurs according to the Protocol.
- iii. The proportion of eligible donor cardiac allografts where the heart is preserved in the correct randomly allocated solution.
- iv. Key outcome completeness
- v. The development of Primary Graft Dysfunction, according to the 2014 ISHLT Consensus Definition(2), within 24 hours of transplant implantation.
- vi. Echocardiographic parameters from trans-oesophageal echo immediately after transplant implantation, including:
 - a. Left Ventricular ejection fraction
 - b. Left ventricular maximal posterior wall thickness
 - c. Maximal septal wall thickness
 - d. Left ventricular function
 - e. Right ventricular function
 - f. The presence/absence of regional wall motion abnormalities
- vii. 30-day all-cause mortality.
- viii. 6-month survival rates, determined at the end of the study.
- ix. Development of the following post-operative complications will be recorded:
 - a. Dysrhythmias (defined by the clinical team) within 30-days of transplant implantation
 - b. Myocardial Infarction (defined according to ESC definitions of myocardial infarction post cardiac surgery) within 30-days of transplant implantation
 - c. Stroke (defined by radiological evidence of ischaemia/haemorrhage and clinical symptoms of stroke) within 30-days of transplant implantation
 - d. Transplant rejection (defined by the clinical team and confirmed on histopathology of biopsy material or post-mortem) within 30-days of transplant implantation
 - e. The need for post-operative renal replacement therapy within 30-days of transplant implantation
 - f. Infection (from any source requiring antibiotic therapy) within 30-days of transplant implantation
 - g. Venous thromboembolism (defined by radiological evidence and need for treatment) within 30-days of transplant implantation
 - h. Re-admission to any UK hospital within 30 days of transplant implantation
 - i. Hyponatraemia within 24 hours of transplant implantation (Na<125mEq/L on any serum laboratory-analysed sample, not blood gas analysis)
- x. Median length of initial ICU stay in hours
- xi. Median length of initial hospital stay in days

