GCP Good Clinical Practice

GDPR General Data Protection Regulation
GMP Good Manufacturing Practice

HRUK Heart Research UK
IB Investigator Brochure
ICF Informed Consent Form

ICH International Conference on Harmonisation of technical

requirements for registration of pharmaceuticals for human

use.

ICU Intensive Care Unit

IMP Investigational Medicinal Product

IMPD Investigational Medicinal Product Dossier

ISF Investigator Site File (This forms part of the TMF)
ISRCTN International Standard Randomised Controlled Trials

Number

LVAD Left Ventricular Assist Device MA Marketing Authorisation

MHRA Medicines and Healthcare products Regulatory Agency

MS Member State

NHSBT NHS Blood and Transplant

NHS R&D National Health Service Research & Development

NIMP Non-Investigational Medicinal Product
NORS National Organ Retrieval Service
PGD Primary Graft Dysfunction
PI Principal Investigator

F-CUSToS Protocol

Version Number 2.0; Dated 30 January 2025

PIC Participant Identification Centre
PIS Participant Information Sheet

PP Potential Participant
QA Quality Assurance
QC Quality Control
QP Qualified Person

RCT Randomised Control Trial REC Research Ethics Committee

RPH Royal Papworth Hospital NHS Foundation Trust

RVAD Right Ventricular Assist Device

SAE Serious Adverse Event SAR Serious Adverse Reaction

SCfCI Sterile Concentrate for Cardioplegia Infusion

SDV Source Data Verification

SNOD Specialist Nurse in Organ Donation SOP Standard Operating Procedure SmPC Summary of Product Characteristics

SSI Site Specific Information

SUSAR Suspected Unexpected Serious Adverse Reaction

TMF Trial Master File

TMG Trial Management Group
TSC Trial Steering Committee
VTE Venous Thromboembolism
WHO World Health Organisation

iii. TRIAL SUMMARY

Trial Title	F easibility study for Randomised Controlled Trial of Cu stodiol-HTK vs S t T homas' solution for cardioplegia and cold static S torage of UK donation after brainstem death hearts in cardiac transplantation.		
Internal ref. no. (or short title)	F-CUSToS		
Clinical Phase	Stage IV		
Trial Design	Single-blind, multi-centre, national, randomised feasibility study.		
Trial Participants	All adult patients undergoing heart transplantation in the UK from a DBD donor.		
Planned Sample Size	50 patients		
Treatment duration	N/A		
Follow up duration	30 days post-transplant implanta	tion	
Planned Trial Period	12 months		
	Objectives	Outcome Measures	

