7.8 Long-term follow-up assessments

Trial closure data collection: After the 31st day after the final recruited participant has undergone their transplant the trial manager will telephone each of the PI to confirm the survival status of each recruited patient and, where a patient has died, the time to death will be measured from the date of their transplant and will be reported for all deaths due to all causes. The cause of death is to be recorded in all instances. The trial manager will also confirm with each PI the total length of in-hospital stay of any patient whose initial ICU or in-hospital stay was longer than 30 days. This should be completed within 4 weeks of the Trial Closure date.

There will be no additional long-term follow-up assessments related to participation in this trial. Long-term follow-up post-transplant is routine and life-long but will not be altered in any way as a result of participation in this trial.

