7.11 End of trial

The trial will end 31 days after the last recruited recipient participant receives their transplant. Day 1 will be considered the day that the participant is admitted to ICU following their transplant implantation procedure, with 31 days counted inclusively and the trial ending at 23:59 on the 31st day.

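### 6-month survival is a secondary endpoint, but the trial closes 31 days after the last transplant, so roughly a third to over 80% of patients will lack 6 months of potential follow-up

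*Protocol*

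**What the plan says.** The Trial Summary and section 3.3.2 both list 6-month survival among the secondary outcomes; section 3.3.2 words it as "6-month survival rates, determined at the end of the study". The timing elsewhere in the protocol is shorter:

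- Section 7.11: "The trial will end 31 days after the last recruited recipient participant receives their transplant".
- The Trial Summary gives 30 days of follow-up after implantation, and the last column of the Appendix 2 schedule is the 30-day follow-up.
- Section 7.8: after day 31 of the final participant, "the trial manager will telephone each of the PI to confirm the survival status of each recruited patient". Time to death is recorded for deaths from any cause, and this is to be finished within 4 weeks of closure. The section adds: "There will be no additional long-term follow-up assessments related to participation in this trial".
- Section 3.3.4 appears to place this endpoint at the end of recruitment, which is earlier still, but the table text is damaged in the copy reviewed.

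On recruitment, section 10.2 states "we anticipate a recruitment rate of 80 patients per year, over a period of 6-12 months" and "1 patient per site per month would result in a 9-month recruitment period". For survival outcomes, section 10.3.3 plans Kaplan-Meier plots and log-rank tests.

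**The concern.** A patient alive at closure has known 6-month status only if transplanted at least 6 months before the survival check. With recruitment over 6 to 12 months and the check 1 to 2 months after the last transplant, many patients cannot meet that condition. This is a matter of data collection: an analysis plan cannot recover follow-up that the protocol does not gather.

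Two things are at stake. First, section 3.3.2 calls the endpoint a rate, and a crude rate would mislead. Early deaths are always known while recent survivors are not, so a rate among patients with known status overstates mortality, and counting the unobserved as alive understates it. Second, a censoring-adjusted estimate at 6 months depends mainly on patients recruited early. Section 4 says this design replicates the larger efficacy trial apart from the primary outcome, so the mismatch could carry forward.

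**Working it through.** **Inputs from the protocol.** Sample size 50 (Trial Summary); six centres, section 4: "The trial will be conducted at all six UK adult cardiothoracic transplant centres"; recruitment 6 to 12 months, with 9 months as the worked case (section 10.2); trial end at 31 days (section 7.11); closing calls up to 28 days later (section 7.8).

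**Assumptions.** Uniform accrual; 1 month = 365.25/12 = 30.44 days, so 6 months = 182.6 days.

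**The plan's own figure.** 50 / (6 centres × 1 per month) = 8.33 months, which rounds up to the stated 9. At 80 per year, 50 patients take 50/80 × 12 = 7.5 months.

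**Formula.** With recruitment lasting R months and the check L months after the last transplant, a patient has 6 months of potential follow-up only if transplanted in the first R + L − 6 months. The share without it is 1 − (R + L − 6)/R = (6 − L)/R.

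- Day 31: L = 31/30.44 = 1.02, so the share is 4.98/R.
- Last permitted call: L = (31 + 28)/30.44 = 1.94, so the share is 4.06/R.

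| Recruitment R (months) | Without 6 months at day 31 | Without 6 months at last permitted call |
|---|---|---|
| 6 | 83% | 68% |
| 7.5 (80 per year) | 66% | 54% |
| 8.33 | 60% | 49% |
| 9 | 55% | 45% |
| 12 | 42% | 34% |

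**Where a majority lacks follow-up.** The share is one half when R = 2 × (6 − L): about 10.0 months at day 31 and about 8.1 months at the last permitted call.

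**Patients with potential follow-up to 6 months.** For R = 9 at day 31, 50 × 0.446 = 22, or about 11 per arm under 1:1 allocation. For R = 12, 50 × 0.585 = 29, or about 15 per arm. These are upper limits on the number at risk at 6 months, because earlier deaths reduce them.

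**If section 3.3.4 means end of recruitment literally.** L = 0 gives 6/R: 100%, 67% and 50% for R = 6, 9 and 12.

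**The case against.** The strongest reply is that the protocol already plans a method suited to this. Staggered entry with administrative censoring is what Kaplan-Meier and log-rank methods are for, and section 7.8 collects status and time to death for every participant. That stands. A reader might infer that the endpoint cannot be delivered at all; the documents do not support this, because a 6-month estimate can be produced, though with heavy censoring.

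A reader might also infer that most patients will lack 6-month status. That holds at the defined trial end with 9 months of recruitment (55%). It fails at 12 months (42%), and at 9 months if all calls fall at the end of the permitted window (45%). Nine months is a worked rate within a stated range. The percentages also describe potential follow-up: a patient who dies before closure has known 6-month status whenever transplanted.

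It is tempting to add that early recruits are unrepresentative because centres are learning a new solution. Sections 1 and 2.1 describe both solutions as in current, routine UK use. St Thomas' accounts for around 90% of transplants, so experience may be uneven, but no learning curve is described.

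The end-of-recruitment timing in section 3.3.4 comes from damaged text and may be loose wording for the final analysis, so little weight should rest on it.

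Finally, the consequence is limited. The secondary hypotheses (3.2), the success criteria (3.3.1) and the monitoring committee's thresholds (7.10) do not use 6-month survival.

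**Conclusion.** The inconsistency is real. The protocol names a 6-month endpoint determined at study end, then closes the trial and makes its only later survival check 1 to 2 months after the last transplant. Over the stated recruitment range, 42% to 83% of patients lack 6 months of potential follow-up at day 31, and 34% to 68% at the last permitted call. No combination within that range brings the share below about a third. These figures rest on uniform accrual; slow early recruitment would raise them.

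The supportable conclusion is that the planned method can yield a 6-month estimate, but one that is heavily censored and dependent on early recruits. It does not affect the primary feasibility outcome or the 30-day outcomes. The point is worth correcting before closure because the remedy is inexpensive.

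**What to change.** Keep the primary and 30-day analyses at the day-31 closure. For 6-month survival, obtain vital status for every participant in one NHSBT Transplant Registry extract taken 6 months after the last transplant. The registry already supplies baseline and operative data (sections 7.6 and 7.7), and section 7.2.4 allows its use after withdrawal unless the participant refuses. It is not currently named as the source for this endpoint, so the sponsor should first confirm that consent covers the extract.

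The cost is one extract and no visits. This endpoint would be reported about 5 months later (183 − 31 = 152 days). If the end-of-trial definition in section 7.11 is itself moved, the trial also stays open that much longer, with its annual reporting duties and beyond the 12-month trial period in the Trial Summary. The 18-month funding period (section v) accommodates the extract: 9 + 6 = 15 months, and 12 + 6 = 18 months, which leaves no slack.

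If later data are not wanted, rename the endpoint as survival to trial closure by Kaplan-Meier and drop the 6-month rate.

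Either way, reconcile the Trial Summary and sections 3.3.2, 3.3.4, 7.8 and 7.11.
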